## 6. CRITERIA FOR SUBJECT WITHDRAWAL AND PREMATURE TERMINATION OF THE STUDY

### 6.1 Subject Withdrawal Criteria

Subjects may be prematurely terminated from study for the following reasons:

1. The subject elects to withdraw consent from all future study activities, including follow-up.
2. The subject is "lost to follow-up" (i.e., no further follow-up is possible because attempts to reestablish contact with the subject have failed).
3. The subject develops a clinical AE, laboratory abnormality, or intercurrent illness which, in the opinion of the investigator, indicates that continued treatment with study therapy and further participation in the study (including obtaining vital status of the subject and islet graft) is not in the best interest of the subject.
4. The development of belatacept is terminated by the manufacturer (BMS).
5. The subject becomes a prisoner or becomes involuntarily incarcerated for treatment of either a psychiatric or physical (e.g., infectious disease) illness.
6. The subject dies.

### 6.2 Study Stopping Rules

#### 6.2.1 Protocol Suspension and Review

Study enrollment at all participating clinical sites will be suspended pending expedited review of all pertinent data by the institutional review board (IRB), the National Institute of Allergy and Infectious Diseases (NIAID), the National Institute of Diabetes and Digestive and Kidney Diseases (NIDDK), and the NIDDK Data Safety Monitoring Board (DSMB), if any one of the following occurs:

1. Any unexpected fatal or life-threatening AE that is possibly, probably, or definitely related to the study treatment regimen (Section 5);
2. **Primary non-function** occurs in 3 or more subjects;
3. There are 6 consecutive study subjects with a c-peptide less than 0.3ng/mL (on random testing, at baseline and 1-3 hrs post MMTT) at 75 days post-transplant;
4. Any event(s) which in the opinion of the Medical Monitor or Protocol Chair indicates the need for DSMB review; or
5. The DSMB recommends termination of protocol enrollment and further transplants on a study-wide basis based on a review of the data and finding evidence that such action is necessary.

After the protocol is placed on hold, no additional transplants within the trial will be performed at any participating clinical site until the CIT Steering Committee and DSMB meet either in

person or by conference call to review in depth the results and circumstances surrounding the islet functional failure or SAE to determine whether the trial enrollment of new subjects and conduct of additional transplants could be safely resumed.

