### 1.4.2 Immunosuppressive Medications

In this trial, we hypothesize that avoidance of the diabetogenic drug, tacrolimus and complete avoidance of the anti-angiogenic drug, sirolimus will create a more favorable environment for islet engraftment and function, and will thus substantially improve the rate of success with single donor transplants and minimize or avoid non-immune toxicities such as hypertension, hyperlipidemia, and nephrotoxicity. The trial is a two-center, prospective pilot study of islet transplantation using a steroid-free, calcineurin-inhibitor-free belatacept-based immunosuppressive medication in 20 subjects with long-standing T1D that is refractory to intensive insulin therapy that meet all additional entry criteria and has given informed consent.

The study medication, belatacept, will be administered using the modified less intensive regimen that was derived from the phase 2 human renal transplant trial and is consistent with the less intensive dosing regimen used in the phase III program. Based on results from the

completed phase 2 study, both the less intensive and more intensive regimens appear acceptable. Both regimens met the primary endpoint of non-inferiority to CsA in acute rejection. Both exhibited subject/graft survival similar to CsA, improved GFR, and a lower incidence of CAN. The less intensive dosing regimen will be augmented with a dose at Day 4 to ensure adequate immunosuppression in the early, immunologically-critical, period. Based on this information we will employ the modified lower intensity regimen when testing belatacept. This should result in achieving target levels consistently without excessive immunosuppression.

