### 1.5.5 Benefits

#### 1.5.5.1 BENEFITS OF ALLOGENIC ISLET TRANSPLANTATION

Successful islet transplantation alleviates T1D patients from life-threatening hypoglycemia and psychosocially debilitating glycemic lability. While the long-term durability of these responses is at present uncertain, they persist for as long as some graft function is maintained, despite the eventual return to insulin therapy in the majority of recipients. This partial function, as indicated by continued c-peptide production, may be present in as many as 80% of recipients after 5 years. Furthermore, as long as graft function is maintained, fear of hypoglycemia and anxiety are significantly lower after islet transplantation. Indeed, T1D subjects in the DCCT who had persistent c-peptide production had a significantly reduced risk of severe hypoglycemia despite intensive insulin therapy. Additionally, while most transplant recipients experience only a temporary reprieve from exogenous insulin therapy, a few have maintained insulin-independent graft function for more than 3 years. Novel strategies aimed at promoting the engraftment or survival of transplanted islets may lead to improved long-term graft function and further the duration of insulin-independence after transplantation, and hopefully lead to reductions in the secondary complications of T1D.

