## 4. STUDY DESIGN

This trial is a prospective, two-center, open-label, pilot study of islet transplantation assessing the safety and efficacy of a steroid-free, calcineurin inhibitor-free belatacept based immunosuppressive medication in subjects with long-standing T1D that is refractory to intensive insulin therapy. The two centers participating in this phase 2 study will also undertake a separate, phase 3 study in islet transplantation, using a standard manufacturing and immunosuppressive regimen. The phase 3 trial, Protocol CIT07, will have inclusion/exclusion criteria and endpoint measures that are identical to those in this phase 2 trial. In order to avoid bias in selection of subjects, eligible subjects will be randomized, prior to transplantation, to participate either in this phase 2 or the multi-center phase 3 study.

Subjects who meet the general inclusion/exclusion criteria will be approached regarding their participation. Subjects who sign informed consent will be enrolled and assigned a unique subject identification number. Subjects will then be formally evaluated for eligibility through the performance of screening visit procedures. More than one visit may be necessary to complete all of the screening procedures. The two participating centers will accrue subjects over a 24 month period and will treat a total of 10 study subjects. No one center will treat more than 12 subjects.

Figure 1: Study Design Schema.

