## 10.4 Sample Size and Power Calculations

The purpose of this pilot study is to estimate the true rate of insulin independence at 75 days. The selected sample size is 10 subjects. The point estimate of the true insulin independence rate will be the proportion of the 10 patients that achieve insulin independence. The precision of the estimate depends on the observed number of subjects achieving insulin independence. The following table displays the confidence intervals that would be computed for each possible outcome. If 5 of the 10 subjects achieve insulin independence then the estimated rate will be 50% and a 95% confidence interval will be 0.1871 to 0.8129. That is, we are 95% confident that the true rate is at least 18.71% and no more than 81.29%. The confidence interval rules out any rate less than 18.71% or greater than 81.29%. If 3 patients (30%) achieve insulin independence, then the confidence interval will rule out any rate less than 6.67% or greater than 65.25%.

*Table 5: Confidence Intervals for each possible outcomes*

Number of Subjects insulin Independent at 75 Days	Estimated Rate	Exact 95% Confidence Interval	
		Lower Bound	Upper Bound
0	0	0	0.3085
1	0.1	0.0025	0.445
2	0.2	0.0252	0.5561
3	0.3	0.0667	0.6525
4	0.4	0.1216	0.7376
5	0.5	0.1871	0.8129
6	0.6	0.2624	0.8784
7	0.7	0.3475	0.9333
8	0.8	0.4439	0.9748
9	0.9	0.555	0.9975
10	1	0.6915	1

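### Suspension rule 3 needs an unbroken run of 6 graft failures among 10 subjects, so it is specific but insensitive: it fires in only 26% to 47% of trials at true failure rates of 70% to 80%

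*Protocol*

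**What the plan says.** Section 6.2.1 lists five events, any one of which puts the whole protocol on hold pending expedited review. Rule 3 is met when "There are 6 consecutive study subjects with a c-peptide less than 0.3ng/mL" "at 75 days post-transplant". Rule 2 is met when primary non-function "occurs in 3 or more subjects"; that is a cumulative count, but the Study Definitions confine primary non-function to days 3 to 7. Rules 4 and 5 leave the decision to the Medical Monitor, the Protocol Chair or the DSMB. The site-level rule in Section 6.2.2 that concerns graft function also covers primary non-function only.

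On trial size, Section 10.4 states: "The selected sample size is 10 subjects". Section 4 agrees: the two centres will "accrue subjects over a 24 month period and will treat a total of 10 study subjects". No reason is given for the number 6, no operating characteristic is given for rule 3, and no Day 75 C-peptide failure rate is named as acceptable or unacceptable.

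**The concern.** Rule 3 is the only numeric trigger in the protocol for graft loss after the first week. Its input is the longest unbroken run of failures, not the number of failures. Under a constant failure rate the order of the failures says nothing about the regimen, yet order decides whether the rule fires. The bar for a reset is low: under the Study Definitions, a basal or stimulated C-peptide of 0.3 ng/mL is already partial function, even in a subject still on insulin.

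At stake is whether new subjects go on being transplanted under a regimen that loses most grafts. A failed graft is not a neutral outcome. Section 1.5.1.3 reports that panel reactive antibody above 20% was found in roughly 84% of recipients who had lost islet function and stopped immunosuppression.

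**Working it through.** **Inputs.** N = 10 (Sections 4 and 10.4); run length 6 and the Day 75 time point (Section 6.2.1); primary non-function on days 3 to 7 (Study Definitions); accrual of 10 subjects in 24 months (Section 4). The true failure rate *p* is an assumption and is varied.

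**The plan's own figures.** Nothing is stated for rule 3 itself. The nearest checkable figures are the exact 95% intervals in Table 5. All 11 rows reproduce as Clopper-Pearson limits for n = 10; for example, 5 of 10 gives 0.1871 to 0.8129. Ten is therefore the size on which the statistics rest.

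**Probability that rule 3 fires.** Take independent subjects with a common *p*, in order of transplant. A qualifying run starts at subject 1 (probability p^6), or at one of subjects 2 to 5 straight after a functioning graft (4 × (1−p)p^6). Two such runs cannot fit in 10 subjects, so the terms add:

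P = p^6 + 4(1−p)p^6 = p^6(5 − 4p)

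At p = 0.7: 0.117649 × 2.2 = 0.2588. Enumerating all 1,024 sequences and a Markov recursion give the same values. The last column drops the ordering and keeps the count, P(X ≥ 6) with X binomial(10, p).

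| True failure rate | Rule 3 as written | 6 failures in any order |
|---|---|---|
| 20% | 0.03% | 0.6% |
| 30% | 0.3% | 4.7% |
| 50% | 4.7% | 37.7% |
| 60% | 12.1% | 63.3% |
| 70% | 25.9% | 85.0% |
| 80% | 47.2% | 96.7% |
| 90% | 74.4% | 99.8% |

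As written, the rule reaches 50% only at p = 0.81 and 80% only at p = 0.92.

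**Given the observed number of failures.** Orderings that escape rule 3: 6 failures, 205 of 210 (98%); 7 failures, 104 of 120 (87%); 8 failures, 27 of 45 (60%); 9 failures, 2 of 10 (20%, when the one functioning graft is subject 5 or 6).

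**Timing.** At even accrual, 10/(24 × 30.4375) × 75 = 1.03 further subjects are transplanted during a 75-day wait, so the earliest trigger comes with about 7 of 10 treated. For someone still to be untreated, the sixth failure must fall by about subject 8. For a run this has probability p^6(3 − 2p): 18.8% at p = 0.7 and 36.7% at 0.8. For 6 failures in any order among 8 it is 28p^6(1−p)^2 + 8p^7(1−p) + p^8. At 0.7 that is 0.2965 + 0.1976 + 0.0576 = 55.2%; at 0.8 it is 0.2936 + 0.3355 + 0.1678 = 79.7%.

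**Rules 2 and 3 together.** Let a share *s* of failures be primary non-function (assumed; the protocol gives no figure) and let those failures count towards both rules. A recursion on current run length and primary non-function count gives the chance that either rule fires:

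| True failure rate | s = 0 | s = 10% | s = 25% | s = 50% |
|---|---|---|---|---|
| 70% | 25.9% | 27.6% | 41.6% | 77.2% |
| 80% | 47.2% | 48.8% | 61.2% | 88.2% |
| 90% | 74.4% | 75.4% | 82.6% | 96.0% |

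**The case against.** The strongest defence is that rule 3 is a backstop in an open-label study of 10 subjects with much other oversight. Rule 4 allows DSMB review to be called for any event. Section 11.1 has the DSMB and IRB review all data periodically. Section 8.2.2 requires graft loss to be reported for all randomized subjects. Section 7.6.1 requires Steering Committee approval before any second transplant. Exposure after a failure is also limited: under Section 5.7.1.2, immunosuppression stops once no further transplant is planned. All of this stands and lowers the stakes. None of it is a numeric trigger, however, and the retransplant check looks at one subject at a time.

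A run rule can also be defended as a detector of sudden deterioration, where order does carry information. The protocol gives no such purpose, and a cumulative count would register the same run.

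Some stronger readings are tempting but unsupported:

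- A reader might infer that the rule cannot separate a good regimen from a bad one. It can: its firing probability goes from 0.03% at 20% failure to 74.4% at 90%. What it lacks is sensitivity.
- A reader might take 9 failures out of 10 without a trigger as typical. It is possible, but 8 of the 10 such orderings do trigger, and rule 2 would act if three of the nine were primary non-function.
- A reader might use the remark in Section 1.5.5.1 that partial function "may be present in as many as 80% of recipients after 5 years" as a benchmark. It is background on earlier recipients at five years, not a Day 75 rate after a first transplant.
- A reader might conclude that the rule was written for a larger trial, since Section 1.4.2 still speaks of "immunosuppressive medication in 20 subjects with long-standing T1D" and Section 4 adds "No one center will treat more than 12 subjects". With 20 subjects rule 3 would fire in 54.4% of trials at 70% failure. The documents do not say where the 6 came from, so this remains a guess.

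**Conclusion.** The concern holds as one of low sensitivity. Rule 3 misses about three in four trials at a 70% failure rate and just over half at 80%. If 10% to 25% of failures are primary non-function, rules 2 and 3 together still fire in only 28% to 42% of trials at a 70% failure rate. A trigger would be strong evidence that grafts are failing; silence would be weak evidence that they are not.

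The figures assume independent subjects, one constant failure rate and complete Day 75 data. Clustering of failures in time would make runs more likely. Because the protocol names no acceptable Day 75 C-peptide failure rate, every rate used is an assumption; the weakness holds across the range up to about 80% failure.

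**What to change.** In Section 6.2.1, rule 3, delete *consecutive* and define the count as cumulative Day 75 graft failures after the first transplant, as rule 2 already does for primary non-function. Naming the first transplant is needed because rule 3 does not say which infusion starts the 75 days, and Section 7.6.1 allows a second transplant before Day 85 after graft failure. The wording should also say whether a graft failure confirmed earlier counts, since the Study Definitions excuse those subjects from the Day 75 metabolic tests. State the operating characteristics at N = 10 beside the rule.

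The table above shows the gain with the count kept at 6. A count of 6 still cannot act before about the seventh transplant, so the sponsor and the DSMB may wish to consider a lower one. For illustration only, a cumulative count of 4 fires in 82.8% of trials at 50% failure, with a pause in 5.0% at 15% and 12.1% at 20%. Which trade-off is right is for them to decide.

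The cost is a short amendment agreed with the DSMB, with no added subjects or procedures. The downside is a small chance of an unnecessary hold, which leads to expedited review and not to termination.

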### **6.2.2 Site Suspension and Review**

Study enrollment and initial islet transplants will be suspended (placed on hold) at a participating clinical site, pending expedited review of all pertinent data by the IRB, the NIAID, the NIDDK, and the NIDDK DSMB, if any one of the following occurs:

1. Any grade 5 AE that is possibly, probably, or definitely related to the study treatment regimen (Section 5); or
2. Two SAEs related to the islet transplant procedure (e.g., bleeding, thrombosis, gall bladder injury); or
3. Two consecutive primary non-functioning transplants (see Study Definitions).

After any site is placed on hold, no additional transplants will be performed at that site until the CIT Steering Committee and DSMB meet either in person or by conference call to review in depth the results and circumstances surrounding the islet functional failure or SAE to determine whether the trial enrollment of new subjects and conduct of additional transplants could be safely resumed at that site, or whether there could be implications for the continuation of the entire proposed pilot protocol also at other affiliated sites testing the same protocol.

In all cases of PNF, no further belatacept will be administered and subjects will be asked to temporarily continue on the standard immunosuppression to decrease the risk of sensitization that could increase the risk of poor outcome should future transplants occur. A tapering schedule will be applied until immunosuppressants are completely discontinued.

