## **5.2 Immunosuppression Medications**

The immunosuppressive agents used for the initial and subsequent islet transplants will be identical.

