#### 5.7.1.2 GRAFT FAILURE

Subjects who experience graft failure will be maintained on their current immunosuppressive regimen as long as a subsequent transplant is possible. If/when it is determined that a subject will not receive a subsequent transplant, then immunosuppression will be stopped and the subject will move to the reduced follow-up schedule (see section 5.7.2).

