#### 5.7.2 Premature Discontinuation of Study Treatment (Transition to “Off-Protocol” Treatment)

Study treatment may be prematurely discontinued for any subject for any of the following reasons:

1. The subject is unwilling or unable to comply with the protocol.
2. The investigator believes that the study treatment is no longer in the best interest of the subject.
3. Graft Failure (see Study Definitions).
4. Any clinical AE, laboratory abnormality, or intercurrent illness which, in the opinion of the investigator, indicates that continued treatment with study therapy is not in the best interest of the subject. The agent(s) to which the event is attributed will be discontinued.
5. The subject becomes pregnant
6. Missing 2 consecutive belatacept infusions
7. The development of belatacept is terminated by the manufacturer (BMS)
8. The subject is imprisoned or compulsorily detained for the treatment of either a psychiatric or physical illness (e.g., infectious disease).

Subjects who prematurely discontinue study treatment will remain in the study until normal termination, for the purpose of monitoring safety and efficacy parameters and will enter the reduced follow-up scheduled outlined in Appendix 5. Data from these subjects will be used in the intent-to-treat analysis. These subjects are permitted to simultaneously enroll in a CIT or site-specific graft failure follow-up protocol, if available.

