### 7.6.1 Second Islet Transplant

Islet transplant recipients with partial islet graft function (see Study Definitions) will be considered for a second islet transplant in the interim between 85 days and 8 months post-initial infusion. Islet transplant recipients with **graft failure** will be considered for a second islet transplant before 85 days post-initial infusion. In addition to meeting the criteria outlined below, approval from the Steering Committee must be obtained in advance. Please refer to the MOP for details on this process, which includes review of the potency testing from the first transplant product and post-transplant clinical data.

In order to be eligible for a **second islet transplant**, the following requirements must be met:

1. Subject received  $\geq 5,000$  IE/kg with the first transplant, but failed to achieve or maintain insulin independence.
2. Subject has been compliant with study monitoring and prescribed immunosuppressive therapy.
3. Subject has no unresolved SAEs.
4. No evidence of progressive renal dysfunction, with blood creatinine rising above 2.0 mg/dL (177  $\mu$ mol/L).
5. No evidence of hypersensitization, allergic responses, or other potentially serious drug reactions to medications required by the protocol.
6. PRA  $\leq 50\%$  by flow cytometry (assessment performed locally) and the alloantibody specificity not cross-reactive with antigen(s) present in the subsequent islet preparation in order to avoid unacceptable antigen(s).
7. Absence of any medical condition that, in the opinion of the investigator, will interfere with a safe and successful second islet transplant.

If graft failure occurs after the second islet transplant, these recipients will be considered **treatment failures** with no islet graft function, and immunosuppression will be withdrawn.

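### After primary non-function of a first transplant, section 6.2.2 stops belatacept and tapers the rest, section 5.7.1.2 keeps the regimen while retransplant is possible, and nothing says which prevails

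*Protocol*

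**What the plan says.** The Study Definitions make PNF a graft failure occurring on Days 3 to 7 after transplant. Graft failure itself requires a random C-peptide below 0.3 ng/mL, confirmed by a mixed-meal test at the core laboratory, with 72 hours allowed for results.

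Three sections then govern such a subject after the first transplant:

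- **Section 6.2.2 (closing paragraph).** "In all cases of PNF, no further belatacept will be administered and subjects will be asked to temporarily continue on the standard immunosuppression". The stated purpose is "to decrease the risk of sensitization that could increase the risk of poor outcome should future transplants occur". It ends: "A tapering schedule will be applied until immunosuppressants are completely discontinued".
- **Section 5.7.1.2.** "Subjects who experience graft failure will be maintained on their current immunosuppressive regimen as long as a subsequent transplant is possible". Only later: "If/when it is determined that a subject will not receive a subsequent transplant, then immunosuppression will be stopped".
- **Section 7.6.1.** Recipients with graft failure "will be considered for a second islet transplant before 85 days post-initial infusion", subject to advance Steering Committee approval. PNF is not excepted. Graft failure after a second transplant leads to withdrawal of immunosuppression.

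Two further sections bear on the point. Section 5.2 opens with "The immunosuppressive agents used for the initial and subsequent islet transplants will be identical". Section 5.7.2 lists graft failure among its grounds, introduced by "Study treatment may be prematurely discontinued for any subject for any of the following reasons".

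**The concern.** Both 6.2.2 and 5.7.1.2 are written as instructions, and a subject with PNF after the first transplant meets the conditions of both. One site could withhold belatacept and start a taper; the other could continue the full regimen while the subject awaits a decision on a second transplant. Each would be following the protocol.

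The choice matters for the patient. The regimen has no steroid and no calcineurin inhibitor. Basiliximab finishes on Day 4 (section 5.2.2), and tacrolimus is allowed only when the mycophenolic acid level is low (sections 5.2.1 and 5.2.3). Without belatacept the subject is left essentially on mycophenolate, which 6.2.2 then tapers. Section 1.5.1.3 reports panel-reactive antibody above 20% in about 84% of recipients who had lost islet function and discontinued immunosuppression, and section 7.6.1 requires 50% or less for a second transplant. The 84% mixes graft loss with drug withdrawal, so it shows why the question matters but does not measure the effect of choosing one rule over the other.

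**Working it through.** No design figure is at issue, so the check sets the rules side by side and then counts the doses they dispute.

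**1. Do both rules apply?** PNF is a subset of graft failure by definition, so 5.7.1.2 and 7.6.1 cover it unless they except it. Neither does. Section 6.2.2 covers every PNF case by its own words. Although it sits under site suspension, it is not confined to suspended sites: a single PNF triggers no suspension, since that takes two consecutive cases at a site (6.2.2) or three subjects study-wide (6.2.1).

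**2. Where do they part?**

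| | 6.2.2 | 5.7.1.2, retransplant still possible |
|---|---|---|
| Belatacept | stopped | continued |
| Other agents | continued temporarily, then tapered to zero | continued |
| Trigger for stopping | PNF itself | a determination that no transplant will follow |

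**3. After which transplant?** Only the first. After a second, 7.6.1 also withdraws immunosuppression, and a third transplant requires partial graft function (7.6.2).

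**4. Which belatacept doses are in dispute?** Section 5.1.2.2 schedules 10 mg/kg on Days 0, 4, 14, 28, 56 and 84. Assume the confirmatory meal test is drawn on the day PNF occurs and takes the full 72 hours:

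- Earliest confirmation: Day 3 + 3 = Day 6, after the Day 4 dose.
- Latest confirmation: Day 7 + 3 = Day 10, before the Day 14 dose even at the early edge of its 2-day window (14 − 2 = Day 12).

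The first disputed dose is therefore Day 14. The graft-failure route in 7.6.1 closes at Day 85, so the last is Day 84. The maximum is 4 doses (Days 14, 28, 56, 84), or 4 × 10 = 40 mg/kg. It is fewer if a second transplant takes place, or is ruled out, earlier.

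**5. Does another section decide it?**

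- Section 5.7.2 is permissive, so it neither requires nor forbids stopping.
- Steering Committee approval under 7.6.1 decides the retransplant, not the dosing while it is awaited.
- Section 5.2 points toward belatacept at a second transplant, which sits badly with the stop in 6.2.2, but it does not name belatacept.

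**6. Which endpoints are touched?** Appendix 1 carries the tests done at graft failure forward to the Day-75 calculations. C-peptide below 0.3 ng/mL then fails the 0.5 ng/mL required for insulin independence, so the subject counts as a primary failure under either rule. The endpoints that can move are the proportion receiving a second transplant (4.1.2.1), regimen change, sensitization and discontinuation of immunosuppression (4.1.2.2), and the objective based on up to three transplants (2.2). With 10 subjects, one subject handled differently moves any such proportion by 1/10 = 10 percentage points.

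**The case against.** The strongest reply is that the specific rule overrides the general one. Section 6.2.2 addresses PNF by name; 5.7.1.2 addresses graft failure at large and is conditional on a further transplant being possible. If PNF ends study therapy, no protocol retransplant is intended, the second sentence of 5.7.1.2 agrees with 6.2.2, and 7.6.1 keeps its use for graft failures from Day 8 to Day 84. The mention of future transplants in 6.2.2 need not mean transplants within this trial: section 7.5 foresees islet transplants outside it, and 1.5.1.3 names a later kidney transplant as the sensitization concern.

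This reading is possible, but the protocol nowhere states it, and 7.6.1 leaves PNF subjects inside the early route.

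A second reply is that belatacept is an investigational agent under 5.1, separate from the immunosuppression medications of 5.2, and that 6.2.2 itself distinguishes it from standard immunosuppression. That stands as a limit on section 5.2: a reader might infer that its identical agents certainly include belatacept, but the sentence supports this without proving it. It does not remove the clash. The synopsis and the primary objective count belatacept within the immunosuppression, and even without it a taper to zero contradicts maintenance, although 6.2.2 gives no start date for the taper.

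Third, the setting limits the damage. Candidacy is decided centrally by a process detailed in the manual of procedures, which is not at hand, and repeated PNF triggers review by the safety board. This makes opposite site decisions on candidacy unlikely. It does not settle the Day 14 dose.

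A reader might also infer that withholding the Day 14 and Day 28 doses meets the ground in 5.7.2 of two consecutive missed infusions. Doses withheld on the protocol's own instruction are not naturally missed, so that item should not be relied on.

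**Conclusion.** Wrong as written: an internal contradiction, of minor to moderate severity. For PNF after the first transplant, 6.2.2 and 5.7.1.2 give incompatible instructions, 7.6.1 does not except PNF, and no section ranks them. At most four belatacept doses are in dispute, together with whether the other agents are tapered or kept. The dose count rests on the scheduled days and on the confirmation timing assumed above.

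The effect is confined to the management and sensitization of a small subgroup and to the second-transplant, regimen-change and discontinuation endpoints. The protocol gives no PNF rate for this regimen, so no frequency can be put on it. A reader might infer a threat to the primary result; the documents do not support that, because the Day-75 endpoint and Table 5 are essentially unaffected.

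**What to change.** Make one rule govern PNF after the first transplant. The choice is the sponsor's:

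- **Option A: 6.2.2 governs.** Add an exception for PNF, with a cross-reference to 6.2.2, in 5.7.1.2. State in 7.6.1 either that PNF subjects are excluded from the route before Day 85, or that belatacept restarts per Figure 2 at the second transplant.
- **Option B: PNF subjects remain candidates on the full regimen.** Limit the belatacept stop and taper in 6.2.2 to PNF subjects for whom it has been determined that no subsequent transplant will follow.

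One clarification can go into the same amendment. Sections 5.1.2.2 and 7.4 spell out belatacept dosing only for repeat transplants after Day 85. Figure 2 counts days from transplant, which suggests that the schedule restarts at an earlier second transplant; if so, a sentence should say it.

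The cost is a wording amendment. It adds no visits, procedures or subjects, and it leaves the sample size, the intention-to-treat principle and the primary analysis unchanged.
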